Appendix B: Pharmacokinetic Analysis

1 Calculation Methods

1.1 Data Handling Conventions

1.1.1 Actual vs Planned Times

Actual sample times will be used for the calculation of pharmacokinetic parameters and for individual concentration-time plots.

Planned sampling times will be used to calculate the concentration-time summary statistics and summary concentration-time plots.

1.1.2 Missing and BQL Concentrations

Missing values will not be used in any way.

For calculation of all pharmacokinetic parameters and individual profile plots, plasma concentrations below the quantifiable limit (BQL) of the assay will not be used for the calculation of PK parameters (except BQL values observed at time points before the maximum concentration, which will be taken as zero).

BQL values observed post dose will be substituted by one half of the lower limit of quantification for calculation of plasma concentration summary statistics. Pre dose values will be taken as zero. The number of imputed values will be included in the summary table.

1.2 AUC Calculations

The AUC will be calculated by a combination of linear and logarithmic methods. The linear trapezoidal method will be employed for all incremental trapezoids arising from increasing concentrations and the logarithmic trapezoidal method will be used for those arising from decreasing concentrations

1.3 Lambda-z Calculations

The apparent terminal phase rate-constant (λ_z) will be estimated by linear regression of logarithmically transformed concentration versus time data. Only those data points

which are judged to describe the terminal log-linear decline will be used in the regression.

During the analysis, repeated regressions are carried out using the last three points with non-zero concentrations, then the last four points, last five, etc. Points prior to C_{\max} are not used. Points with a value of zero for the concentration are excluded. For each regression, an adjusted R^2 is computed. The λ_z using the regression with the largest adjusted R^2 is selected. If the adjusted R^2 does not improve, but is within 0.0001 of the largest adjusted R^2 value, the regression with the larger number of points is used. λ_z must be positive, and calculated from at least three data points.

For non-compartmental analysis uniform weighting will be applied.

1.4 Observed v Predicted Values

For parameters dependent on λ_z , the ‘predicted’ rather than the ‘observed’ parameters will be calculated.

The ‘predicted’ parameters are calculated using \hat{C}_t (the predicted value of the concentration at time t_n); whilst the ‘observed’ parameters use the last observed concentration.

2 General Considerations for Data Analysis

2.1 Derived and transformed data

In general, concentration and concentration-related quantities, rate constants and half-lives (e.g. C_{\max} , AUC, $t_{1/2}$ and MRT) will be analysed after logarithmic transformation. Logarithmic transformations will use natural logarithms (\log_e). A list of those parameters that will be log transformed are given below.

2.2 Summary data

Means at any time will only be calculated if at least 2/3 of the individual data are measured and are above the lower of quantification (LLOQ).

3 Parameter Definitions

3.1 Plasma Parameters

3.1.1 Emodepside

Text Symbol	Definition	Calculation	Typical Units	Log Transform	WNL	CDISC Controlled Terminology	TFL Symbol
Concentrations and times							
C_{\max}	Maximum (peak) plasma concentration	The maximum (peak) plasma concentration will be obtained directly from the concentration-time data.	ng/mL	Y	Cmax	CMAX	C_{\max}
C_{\max}/Dose	Dose-normalised C_{\max} to infinity	The dose-normalised C_{\max} will be calculated as $C_{\max}/\text{Dose administered}$	(ng/mL)/mg	Y	C_{\max_D}	CMAXD	C_{\max}/D
$C_{\max,\text{norm}}$	Observed maximum plasma concentration corrected by dose and body weight	The C_{\max} normalised by dose and body weight will be calculated as $C_{\max}/(\text{Dose administered} * \text{body weight})$	(ng/mL)/(mg*kg)	Y	N/A	CMAXWD	$C_{\max,\text{norm}}$
t_{\max}	Time to reach maximum (peak) plasma concentration	The first time of maximum (peak) plasma concentration will be obtained directly from the concentration-time data.	h	N	Tmax	TMAX	t_{\max}
Half-life							
λ_z	Terminal rate constant	The apparent terminal phase rate-constant (λ_z) will be estimated by linear regression of logarithmically transformed concentration versus time data.	1/h	Y	Lambda_z	LAMZ	λ_z
Point terminal	Number of points for Lambda z	The number of time points used in calculating Lambda z	-	-	No_points_lambda_z	LAMZNPT	npts
$t_{1/2,0-7d}$	Terminal half-life	The terminal half-life calculated from the terminal slope of the log concentration-time curve, as follows: $t_{1/2} = \frac{\log_e 2}{\lambda_z}$	h	Y	HL_Lambda_z	LAMZHL	$t_{1/2,0-7d}$
$t_{1/2,0-24h}$	Dominant half-life	The half-life calculated from the terminal slope of the log concentration-time (0-24h) curve, as follows: $t_{1/2} = \frac{\log_e 2}{\lambda_z}$	h	Y	HL_Lambda_z	LAMZHLD	$t_{1/2,0-24}$

Text Symbol	Definition	Calculation	Typical Units	Log Transform	WNL	CDISC Controlled Terminology	TFL Symbol
Areas under the curve							
AUC _{last}	Area under the plasma concentration-time curve from time zero to time of last measurable concentration	The area under the concentration-time curve from zero time (pre-dose) to the time of last quantifiable concentration will be calculated using the (specified) trapezoidal method.	h*ng/mL	Y	AUC_last	AUCLST	AUC _{last}
AUC _{0-7d}	Area under the plasma concentration-time curve from time zero to 7 days	The area under the concentration-time curve from zero time (pre-dose) to 7 days will be calculated using the (specified) trapezoidal method. If λ_z is not estimable, a partial AUC is not calculated (when $t_{last} < t$).	h*ng/mL	Y	User specified area	AUCINT	AUC _{7d}
AUC _{0-7d} /Dose	Dose-normalised AUC from time zero to 7 days	The dose-normalised AUC from time zero to 7 days will be calculated as AUC _{0-7d} /Dose administered	(h*ng/mL)/mg	Y	N/A	AUCINTD	AUC _{7d} /D
AUC _{0-7d,norm}	Area under the concentration-time curve from time zero to 7 days corrected by dose and body weight	The AUC from time zero to 7 days normalised by dose and body weight will be calculated as AUC _{0-7d} /(Dose administered*body weight)	(h*ng/mL)/(mg*kg)	Y	N/A	AUCINTWD	AUC _{7d,norm}
Clearance, volume of distribution and mean residence time							
MRT _{last}	Mean Residence Time	The mean residence time will be calculated using: $MRT = \frac{AUMC_{last}}{AUC_{last}}$	h	Y	MRTlast	MRTEVLST	MRT _{last}

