vision, photophobia (“Increased ocular light sensitivity”), visual impairment (“distorted contrast perception”, “distorted colour perception”) reported by 8 out of 47 subjects receiving emodepside were considered as treatment-related by the Investigator. Also of note, at the highest dose (40 mg), lightheadedness (n=1), dizziness (n=1) or headache (n=1) were reported concomitantly to blurred vision.

None of the volunteers met any of the protocol-specified withdrawal criteria with regards to treatment and overall tolerability to emodepside has been acceptable up to 20 mg. The presence of post-dose visual disturbances in subjects of Cohort 8 receiving either 40 mg solution or placebo may warrant some concern and escalation was stopped at this dose level.

The pharmacokinetic results obtained so far show that T_{max} for the LSF solution is consistently about 1 h post-dose when fasted. Mean C_{max} and AUC for the LSF solution have been roughly dose-proportional, with low to moderate inter-individual variability. The plasma half-life during the first 24 h is very short for a single dose of emodepside. After 3, 7, 16 and 47 h the maximum plasma concentration is reduced to 50%, 25%, 12.5% and 6.25% respectively. Terminal plasma half-life is 523 h. Although data of Cohort 9 (which was treated with a single dose of emodepside with food) are still under review, administration of the LSF of 10 mg with a high fat, high-calorie meal resulted in a clinically relevant food effect with a reduction of AUC to ~67%, C_{max} to 42% and a delay of the T_{max} up to 2.33 h. Therefore, the recommendation of administration of the emodepside (LSF) under fasted conditions is given.

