3.4. Rationale of study design

The study will be performed in a randomized, open-label, parallel group design.

The open design of the trial has the important disadvantage that both investigator and subjects are aware that active treatment is being given, and there is no placebo. The possibility of bias must therefore be taken into account in the assessment of AEs in particular. However, the primary objective of the study is to compare the PK of emodepside after different formulations, which will be assessed using an objective test measured by an external laboratory. Relative bioavailability and food effect form part of the PK assessment. Most of the other assessments are also objective, either because they are measured by a laboratory or are measured using automated means (HR, BP, and ECG).

After a single dose, emodepside is rapidly absorbed and peak plasma concentrations occur within a few hours after dosing. There is a short half-life in the first 24 h

(distribution/elimination phase) followed by a long terminal elimination half-life ($t_{1/2}$ >500 h). Crossover designs are attractive because they can enhance the power of a trial to distinguish between treatments; that is because within-subject variability is generally less than between-subject variability. However, crossover designs are subject to carryover of effects from one treatment to the next, especially if the elimination half-life is long. Because of this, a parallel group design was chosen for this study and PK samples will be taken at the Follow-up Visit (168 h after dosing). Treatments in Part 1 will be randomized to reduce the likelihood of period or seasonal effects confounding the study assessments. Part 2 will also be randomized if both treatments are tested.

The study will be performed in healthy male Caucasian volunteers, in order to avoid ethnic and sex differences that may increase pharmacokinetic variability.

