8.9. PK assessments

Blood samples for assay of emodepside will be collected at the time points indicated in the Schedule of assessments (Section 5). The exact date and time of PK blood sampling will be recorded in the CRF.

Blood samples for emodepside assay will be taken from either arm. Samples will be collected either via a cannula or by venepuncture. After processing, samples will be frozen and transported on dry ice to the Bioanalysis Laboratory. Detailed instructions for collection, processing, storage, and transport of samples will be provided in the Study Procedures Manual. Blood volumes for PK samples are shown in Table 4.

Plasma will be analyzed for emodepside using a validated assay method. Full details of the method will be presented in a separate document and all the results will be reported in the bioanalytical report at the end of the study. On the Profile Day (Day 0), frequent blood samples will be collected for PK estimation and emodepside plasma concentrations. The following PK parameters of emodepside will be derived for each subject:

Pharmacokinetic parameters

Text Symbol	Definition	Calculation
Concentrations and times		
C_{\max}	Maximum (peak) plasma concentration	The maximum (peak) plasma concentration will be obtained directly from the concentration-time data.
C_{\max}/Dose	Dose-normalised C_{\max}	The dose-normalised C_{\max} will be calculated as C_{\max} / Dose administered
$C_{\max,\text{norm}}$	Observed maximum plasma concentration corrected by dose and body weight	The C_{\max} normalised by dose and body weight will be calculated as $C_{\max} / (\text{Dose administered} * \text{body weight})$

Text Symbol	Definition	Calculation
t_{\max}	Time to reach maximum (peak) plasma concentration	The first time of maximum (peak) plasma concentration will be obtained directly from the concentration–time data.
Half-life		
λ_z	Terminal rate constant	The apparent terminal phase rate-constant (λ_z) will be estimated by linear regression of logarithmically transformed concentration versus time data.
$t_{1/2,0-24h}$	Dominant half-life	The half-life calculated from the terminal slope of the log concentration-time curve (0–24 h), as follows: $t_{1/2} = \frac{\log_e 2}{\lambda_z}$
$t_{1/2}$	Terminal elimination half-life	The terminal half-life calculated from the terminal slope of the log concentration-time curve, as follows: $t_{1/2} = \frac{\log_e 2}{\lambda_z}$

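### The half-life labelled terminal comes from 168 h of sampling against a documented 523 h, so it is biased short and should be relabelled as an apparent 0-7 day value

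*SAP*

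**What the plan says.** Protocol 1.4 reports from the first-in-human study that "Terminal plasma half-life is 523 h". Protocol 3.4 describes a short early half-life "followed by a long terminal elimination half-life" above 500 h, and gives the long half-life as the reason for a parallel-group design. The last PK sample is at 168 h (Day 7).

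SAP Appendix B 3.1.1 describes t1/2,0-7d as "The terminal half-life calculated from the terminal slope of the log concentration-time curve", computed as ln 2 / lambda-z. In Protocol 8.9 the parameter appears as t1/2, without the 0-7d suffix, under the label "Terminal elimination half-life".

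SAP Appendix B 1.3 sets out how lambda-z is found: "repeated regressions are carried out using the last three points with non-zero concentrations, then the last four points, last five, etc". The fit with the largest adjusted R-squared is chosen, and a fit within 0.0001 of it is preferred if it uses more points. At least three points and a positive lambda-z are required. The same section restricts the regression to points judged to lie on the terminal log-linear decline, but gives no criterion, minimum time span or fixed window for that judgement.

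**The concern.** A window of about a third of a half-life carries little information on the slope of that phase. With ordinary concentration error the late points look nearly flat and their adjusted R-squared is low. A rule that rewards high adjusted R-squared then favours longer runs that reach into the steeper distribution phase. The result mixes phases but is labelled terminal.

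At stake is what a reader may conclude. A report giving a terminal half-life well below 523 h would contradict Protocol 1.4 and 3.4 without explanation. Half-life also has practical uses: Protocol 4.2, exclusion criterion 1, counts five half-lives of a previous trial's drug. Five times 523 h is 2,615 h, or 109 days. Five times 117 h (the middle simulated value below) is 585 h, or 24 days.

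**Working it through.** **Inputs from the documents.** Terminal half-life 523 h. Decline after the peak: "After 3, 7, 16 and 47 h the maximum plasma concentration is reduced to 50%, 25%, 12.5% and 6.25% respectively" (Protocol 1.4). Tmax "for the LSF solution is consistently about 1 h post-dose when fasted". There are 18 PK samples: pre-dose plus 17 post-dose times, the last six at 24, 36, 48, 72, 120 and 168 h with 36 h onward being the five after 24 h. The 523 h figure cannot be re-derived, because the first-in-human concentrations and sampling length are not given. It is taken as true.

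**Information in the window.**
- 168/523 = 0.32 of a half-life.
- Fall of a pure 523 h phase: 1 − 2^(−168/523) = 20% over 0-168 h; 1 − 2^(−120/523) = 15% over 48-168 h; 1 − 2^(−96/523) = 12% over the last three samples (72, 120, 168 h).
- True slope: ln 2/523 = 0.00133 per h. For the last three samples the sum of squared time deviations is 48² + 0 + 48² = 4,608. With 10% log-scale error the standard error of the slope is 0.10/√4,608 = 0.00147 per h, larger than the slope itself.
- The successive halvings in Protocol 1.4 take about 2, 4, 9 and 31 h, so the earlier points are far steeper.

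**Simulation of the SAP rule.** Multi-exponential profiles were fitted through 100% at 1 h and 50, 25, 12.5 and 6.25% at 3, 7, 16 and 47 h, with the last phase fixed at 523 h. They were sampled at the scheduled times, with 4,000 subjects per cell. Two inputs are assumptions: log-normal error of 5, 10 or 15%, and the share of Cmax carried by the 523 h phase. That share is at most about 6.6%, since 6.25% × 2^(46/523) = 6.6%.

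Median reported half-life (h) at 5 / 10 / 15% error:

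| Share of Cmax | Rule searching back to Cmax | Only points from 48 h on |
|---|---|---|
| 1% | 59 / 58 / 57 | 60 / 60 / 60 |
| 2% | 68 / 68 / 66 | 73 / 74 / 74 |
| 3% | 99 / 94 / 89 | 105 / 105 / 102 |
| 4% | 141 / 125 / 110 | 150 / 146 / 145 |
| 5% | 216 / 161 / 123 | 234 / 219 / 205 |
| 5.5% | 264 / 175 / 121 | 306 / 279 / 253 |
| 6% | 313 / 195 / 114 | 373 / 334 / 292 |
| 6.3% | 354 / 198 / 71 | 429 / 370 / 325 |

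In the middle column all 24 medians are below 523 h. They run from 57 h (523/57 = 9.2-fold short) to 354 h (523/354 = 1.5-fold), with a middle value of 117 h (4.5-fold). Of the 24, 21 are more than 2-fold short and 17 more than 3-fold. The most favourable case tried, a 6.3% share with almost no error, gives 497 h (523/497, about 1.1-fold).

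**Spread from point selection.** At a 6.3% share and 10% error, the number of points chosen runs from 3 to 14 (10th to 90th percentile) and the interquartile range of the half-life is 47-294 h.

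**Effect on AUC0-7d.** Lambda-z enters only if the last quantifiable time is before 7 days. The Day 7 window is ±3 h (Protocol 8.8), so a subject with a quantifiable Day 7 sample inside that window needs at most 3 of 168 h extrapolated (1.8% of the interval), at a small fraction of Cmax.

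**The case against.** **The judgement clause.** Only points judged to be on the terminal decline may be used, so a fully automatic search back to Cmax may be unfair to the plan. This partly stands. If the profile switches to the 523 h phase at 47 h and points are restricted to 48 h onward, simulated medians are 498, 422 and 339 h at 5, 10 and 15% error, or 1.05-, 1.24- and 1.54-fold short. But the clause has no criterion, and the right-hand column above shows that the same restriction leaves a shortfall of about 2- to 5-fold when the slow phase is 3-5% of Cmax.

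**Disclosure.** The symbol names the 0-7d window, lambda-z is already described as apparent, the number of points is a reported parameter, and Listing 16.2.6.3 plots every regression line. That is useful, but the definition beside the symbol still says terminal, and Protocol 8.9 drops the suffix.

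**Consequences.** The endpoint is exploratory, no half-life comparison between formulations is planned, and nothing in the documents says a later study will take washout from this estimate. All of that stands and limits the weight of the point.

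**Stronger readings.** A reader might infer that the value will typically be several-fold too short. The documents do not support a single factor, because they give neither the error nor the slow-phase share. A reader might also infer that a fixed 48-168 h window cures the problem. It would use the same points for everyone but still not recover 523 h in general, and it can fail outright. Its sum of squared time deviations is 54² + 30² + 18² + 66² = 8,496, so the chance of a non-positive slope on a pure 523 h phase is Φ(−0.00133 × √8,496 / error), about 1%, 11% and 21% at 5, 10 and 15% error. Lambda-z would then not be estimable. Under SAP Appendix B 3.1.1, such a subject whose last sample fell before 168 h would lose AUC0-7d, a primary endpoint.

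**Conclusion.** The point holds as one of labelling and interpretation. The design cannot deliver a terminal half-life of the documented size, and the selection rule biases the reported value downward in every case tried. The size runs from about 1.1-fold to 9-fold short. It depends on concentration error, on the share of Cmax in the 523 h phase, and on how the judgement clause is applied. It also assumes that 523 h is correct and that the tablets decline like the first-in-human profile, which is described for the solution. The primary comparisons are hardly touched, so this is a minor but worthwhile correction.

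**What to change.** 1. In SAP Appendix B 3.1.1 and Protocol 8.9, relabel the parameter: apparent half-life over the 0-7 day sampling window (not terminal). Use the 0-7d symbol in both.
2. State there and in the study report that terminal half-life is not estimable from this study, and that the value must not be compared with 523 h or used for washout or accumulation.
3. Show the start and end time of each subject's regression beside the number of points already reported, so the effect of point selection can be seen.
4. Leave the lambda-z used for AUC0-7d unchanged. If a common fixed window is wanted, report it only as a supplementary apparent half-life, and note that some subjects will have no positive slope.

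The cost is wording in two documents and an added time range in the parameter listing. No samples or visits change, and the primary analysis is unaffected.

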4.1. Inclusion criteria

Subjects must meet **all** of the following inclusion criteria to be eligible for enrolment into the study:

1. Male, Caucasian volunteers, deemed healthy based on a clinical history, physical examination, ECG, vital signs, and laboratory tests of blood and urine.
2. 18 to 45 years of age
3. Normal body weight (Body Mass Index (BMI); Quetelet index) in the range 18.0 to 30.1 kg/m² at screening
4. Mean blood pressure and heart rate (from the triplicate readings) in the supine position at the screening assessment within the following ranges:
 - a. 90–140 mm Hg systolic BP
 - b. 60–90 mm Hg diastolic BP
 - c. 45–100 beats/min HR
5. Sufficient intelligence to understand the nature of the trial and any hazards of participating in it. Ability to communicate satisfactorily with the Investigator and to participate in, and comply with the requirements of, the entire trial
6. Willingness to give written consent to participate, after reading the information and consent form, and after having the opportunity to discuss the trial with the Investigator or his delegate
7. Willingness to give written consent to have data entered into The Overvolunteering Prevention System (TOPS)
8. Willingness to follow contraception requirements of the study, from the first dose of the IMP until 90 days after dosing and inform HMR as soon as possible if partner becomes pregnant in the 90 days after dosing.

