Points terminal	Number of points for λ_z	The number of time points used in calculating λ_z
Areas under the curve		
AUC_{last}	Area under the plasma concentration-time curve from time zero to time of last measurable concentration	The area under the concentration-time curve from zero time (pre-dose) to the time of last quantifiable concentration will be calculated using the (specified) trapezoidal method.
AUC_{0-7d}	Area under the plasma concentration-time curve from time zero to 7 days	The area under the concentration-time curve from zero time (pre-dose) to 7 days will be calculated using the (specified) trapezoidal method. If λ_z is not estimable, a partial AUC is not calculated (when $t_{\text{last}} < t$).
AUC_{0-7d}/Dose	Dose-normalised AUC from time zero to 7 days	The dose-normalised AUC from time zero to 7 days will be calculated as $AUC_{0-7d}/\text{Dose administered}$
$AUC_{0-7d,\text{norm}}$	Area under the concentration-time curve from time zero to 7 days corrected by dose and body weight	The AUC from time zero to 7 days normalised by dose and body weight will be calculated as $AUC_{0-7d}/(\text{Dose administered} * \text{body weight})$
Mean residence time		
MRT_{last}	Mean Residence Time	The mean residence time will be

Text Symbol	Definition	Calculation
		calculated using: $MRT = \frac{AUMC}{AUC_{last}}$

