Subjects who withdraw, or are withdrawn from the study, may be replaced at the discretion of the Investigator upon consultation with the Sponsor.

Furthermore, the Investigator may withdraw a subject for the following reasons:

- clinically significant intercurrent illness which could compromise the safety of the subject or the scientific value of the trial
- need for, or use of, contraindicated medication which could compromise

the safety of the subject or the scientific value of the trial

- withdrawal of consent
- significant non-compliance of the subject with the requirements of the trial

If a subject is withdrawn, the Investigator will make all necessary arrangements to ensure that the subject receives the appropriate treatment for the relevant medical condition.

A subject should be withdrawn from the study treatment if, in the opinion of the Investigator, it is medically necessary, or if it is the wish of the subject.

11. Data Analysis and Statistical Methods

Detailed methodology for summary and statistical analyses of the data collected in this study will be documented in a Statistical Analysis Plan. This document may modify the plans outlined in the protocol; however, any major modifications of the primary endpoint definition and/or its analysis will also be reflected in a protocol amendment.

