4.2.3 Exploratory Endpoints

- Pharmacokinetic:
 - $AUC_{0-7d,norm}$, $C_{max,norm}$, $t_{1/2,0-24h}$, $t_{1/2,0-7d}$, t_{max} , MRT, points terminal

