12.2 Derived and Transformed Data

Baseline will be considered to be the latest value obtained before study drug administration (e.g. Day 0, pre-dose; or Day -1 if not recorded pre-dose; or Screening if not recorded elsewhere (e.g. body weight)).

Laboratory data will be reported in standard units. Out-of-range laboratory tests may be repeated. If a test is out-of-range at a baseline time point and repeated before dosing, the latest repeat value before dosing will be used as baseline. However, if a test is out-of-range and repeated at any other time during the study, the out-of-range value (not the repeat value) will be included in statistical summaries.

TriPLICATE ECG and vital sign measurements will be made at pre-dose on Day 0 and the mean of the three measurements for each subject will be used as their baseline value for that session.

The pharmacokinetic parameters to be derived are given in Appendix B.

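### AUC0-7d,norm and Cmax,norm divide by dose times body weight, so these two exploratory parameters gain a weight factor and are not exposure per mg/kg

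*SAP*

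**What the plan says.** Protocol 8.9 defines Cmax,norm as "Observed maximum plasma concentration corrected by dose and body weight". For the area it states: "The AUC from time zero to 7 days normalised by dose and body weight will be calculated as" AUC0-7d over the product of dose and weight. SAP Appendix B 3.1.1 repeats both definitions. It calls AUC0-7d,norm "Area under the concentration-time curve from time zero to 7 days corrected by dose and body weight" and prints the denominator as "Dose administered*body weight". The SAP's abbreviation list describes both in the same terms.

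The SAP units column gives ng/mL and h×ng/mL, each over mg×kg. Formula and units therefore agree, and a division sign lost in PDF conversion is ruled out. Neither document explains why dose is multiplied by weight.

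Both parameters sit under "4.2.3 Exploratory Endpoints" in the SAP and under the exploratory endpoints in Protocol 2.2.3. They would appear in the PK parameter summaries (Tables 14.2.2 and 14.2.3) and in Listing 16.2.6.2.

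**The concern.** Every subject receives a flat dose, 5 mg in Part 1 and 10 mg in Part 2, so a heavier man receives fewer mg per kg. Putting subjects on a common dose-per-kg footing means multiplying exposure/dose by weight. The written formula divides by it and so adjusts in the opposite direction.

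The Protocol's other weight-related quantities are per kg: Protocol 1.3 gives animal doses in mg/kg, clearance in L/(kg×h) and volume in L/kg. With an AUC to infinity, AUC × weight/dose would be the reciprocal of apparent clearance per kg. AUC/(dose × weight) would be the reciprocal of clearance multiplied by weight, which neither document uses anywhere else.

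The SAP names no WinNonlin output for either parameter (the column reads N/A), so they will presumably be programmed from the written formula. Values labelled as weight-corrected would then reach the study report with a weight dependence added.

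**Working it through.** The documents give no numerical value for these parameters, so there is no figure to reproduce. The check is algebra plus illustration.

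**Inputs from the documents**
- BMI limits (Protocol 4.1): "Normal body weight (Body Mass Index (BMI); Quetelet index) in the range 18.0 to 30.1" kg/m².
- First-in-human 5 mg LSF AUClast (Protocol 3.4): mean 1736.2 ng×h/mL, CV 22.6%. It stands in for AUC0-7d and comes from a small cohort.
- 12 subjects per arm.

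**Assumptions (not in the documents)**
- Individual body weights.
- A body-weight CV of 10–15%.
- An exponent b, with exposure/dose varying as weight^(−b), for b from 0 to 1.

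**1. The two definitions.** Let X be exposure, D dose and W weight. As written: X/(D×W). Per mg/kg: X/(D/W) = X×W/D. Written ÷ per mg/kg = 1/W². Written ÷ (X/D) = 1/W. Neither ratio depends on b.

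**2. Same exposure, different weights** (AUC 1736.2, D = 5 mg, weights assumed):

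| Weight (kg) | AUC/D | As written | Per mg/kg |
|---|---|---|---|
| 50 | 347.24 | 6.945 | 17,362 |
| 70 | 347.24 | 4.961 | 24,306.8 |
| 100 | 347.24 | 3.472 | 34,724 |

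The written value falls with weight and the per-mg/kg value rises.

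**3. Weight dependence.** X/D varies as W^(−b), the written metric as W^(−(1+b)) and the per-mg/kg metric as W^(1−b). At b = 0 the written metric creates a weight effect, and for b > 0 it enlarges the existing one. It would reduce the effect relative to X/D only if b were below −0.5, that is, if exposure rose with weight. The per-mg/kg metric removes the effect at b = 1 and reduces it relative to X/D only if b > 0.5.

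**4. Pair of subjects.** At equal height the BMI limits give r = 30.1/18.0 = 1.672 and r² = 2.796. The lighter/heavier ratio is r^b for X/D, r^(1+b) as written and r^(b−1) per mg/kg:

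| b | X/D | As written | Per mg/kg |
|---|---|---|---|
| 0 | 1.00 | 1.67 | 0.60 |
| 0.5 | 1.29 | 2.16 | 0.77 |
| 0.75 | 1.47 | 2.46 | 0.88 |
| 1 | 1.67 | 2.80 | 1.00 |

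For 60 v 90 kg (r = 1.5) and the same b: as written 1.50, 1.84, 2.03, 2.25; per mg/kg 0.67, 0.82, 0.90, 1.00.

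**5. Between-subject CV.** On the log scale v = ln(1 + 0.226²) = 0.0498, and vw = ln(1 + CVw²) = 0.00995 (CVw 10%) to 0.02225 (15%). Written variance = v + (1+2b)vw. Per-mg/kg variance = v + (1−2b)vw. CV = √(exp(variance) − 1). Ranges run from CVw 10% to 15%:

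| b | As written | Per mg/kg |
|---|---|---|
| 0 | 24.8–27.3% | 24.8–27.3% |
| 0.5 | 26.9–31.4% | 22.6% |
| 1 | 28.8–35.2% | 20.2–16.7% |

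**6. Arm level.** The standard error of the difference in mean ln W between two arms of 12 is √(2×vw/12) = 0.041 to 0.061. A one-standard-error imbalance moves the written geometric-mean ratio about 4–6% beyond that of X/D.

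**The case against.** The strongest objection is that the standard is inferred. Neither document mentions mg/kg for these parameters, and the formula, the units and the two documents all agree with one another. That is correct: this is a shared error of definition, with no slip in calculation and no conflict between Protocol and SAP. The formula still does not do what its label says. A dose-and-weight correction of a flat dose is naturally read as per mg/kg, and no reason is offered for the product.

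Four further points stand, as limits on the finding:
- **Reach.** SAP 15.2 uses AUC0-7d/Dose and Cmax/Dose for bioavailability and food effect, and AUC0-7d and Cmax for dose proportionality. No planned comparison uses these two parameters.
- **Size.** The 2.80-fold figure is for an extreme pair. The parameters are summarised by arm, where 4–6% is the more representative figure.
- **The replacement.** Multiplying by weight is not guaranteed to remove the weight effect. With b unknown it helps relative to X/D only above 0.5, and at b = 0 its CV equals that of the written metric.
- **Recoverability.** The formula is stated openly and the SAP promises complete data listings, so a reader could recompute the values. That limits the harm but does not make the tabulated values correct.

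**Conclusion.** The concern holds. Following the text would put values with a weight factor added into Tables 14.2.2 and 14.2.3 and Listing 16.2.6.2 under a label saying that weight has been corrected for. The 1/W² discrepancy from a per-mg/kg value is exact. The 2.80-fold contrast needs only the BMI limits and equal height. The CVs rest on the assumed b and weight CV and on AUClast as a stand-in, and the 4–6% arm-level shift rests on the assumed weight CV. That per-mg/kg was the intended target is an inference.

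This should be fixed, but the consequence is confined to descriptive output for two exploratory parameters. No primary endpoint, model or acceptance assessment changes.

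**What to change.** In SAP Appendix B 3.1.1, define AUC0-7d,norm = AUC0-7d × body weight/dose and Cmax,norm = Cmax × body weight/dose, with units (h×ng/mL)/(mg/kg) and (ng/mL)/(mg/kg). If division by weight was intended, give the reason and relabel both parameters instead.

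State which weight is used. SAP 12.2 says "Baseline will be considered to be the latest value obtained before study drug administration", which selects Day −1 because both schedules measure weight then, with Screening as the fallback. The same sentence cites body weight as an example of a variable that may be recorded only at Screening, so that example should be tidied.

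Align Protocol 8.9. Protocol Section 11 says of the SAP: "This document may modify the plans outlined in the protocol", and it requires an amendment only for major changes to the primary endpoint or its analysis. The SAP correction can therefore come first.

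The cost is two formulas and two unit entries. No new data are needed, since weight, AUC and Cmax are already collected or derived. The Protocol text change must still be documented and handled under Protocol Section 14.
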